2. OVERALL SYNOPSIS OF THE CLINICAL INVESTIGATION

Clinical investigation title:	Impact of Bridge™ device as a non-pharmacological approach to treat opioid withdrawal in opioid use disorder (OUD) subjects in an inpatient treatment center
Study objective(s):	The purpose of this prospective study is to investigate the efficacy of the Bridge™ device in reducing the symptoms of opioid withdrawal in a blind comparison to a sham device.
Investigational device(s):	Bridge™ active and sham devices
Number of subjects:	48 total subjects
Inclusion criteria:	
• Participant able to provide written informed consent• Participant is 18 to 65-years old• Participant has confirmed opioid use disorder (OUD) as defined by the Diagnostic and Statistical Manual of Mental Disorders-5• Participants is entering an OUD treatment program
Exclusion criteria:	
• Participant requires tapering from another substance at entry to treatment• Participant is pregnant or lactating• Participant has a history of hemophilia or psoriasis vulgaris• Participant has a cardiac pacemaker implant device• Participant has irritated or broken skin at the site of intended device placement• Participant is currently participating in, or was enrolled in another clinical trial within the last 30 days• Participant has a history of poor wound healing• Participant has a severe autoimmune disease or uncontrolled diabetes• Participant has an open wound/abscess infection/MRSA• Participant has a history of a chronic pain in the last 90 days• Participant has a serious medical condition which in the judgment of the principal investigator or his/her designee would make study participation unsafe, or would make intervention compliance difficult• Participant has a psychiatric illness (bipolar disorder, schizophrenia, or other psychotic disorder, active suicidal ideation with a plan within the last month or suicide attempt)
Groups and Randomization:	Two groups randomized at enrollment Group 1: Interventional arm - Active device Group 2: Control arm - Sham device
Duration of the clinical investigation:	2 years for enrollment completion
Study endpoint(s):	
PRIMARY:
 
• Assess change in Clinical Opiate Withdrawal Scale (COWS) score 
SECONDARY:
 
• Assess change in Subjective Opiate Withdrawal Scale (SOWS) score

Impact of Bridge™ device as a non-pharmacological approach to treat opioid withdrawal in opioid use disorder (OUD) subjects in an inpatient treatment center

DENE0001

3. DESCRIPTION OF THE INVESTIGATIONAL DEVICE

Bridge™ is a small electrical percutaneous nerve field stimulator device that contains a battery-powered chip and wires that are applied around a subject's ear. It is an FDA-cleared⁽¹⁾, drug-free, non-surgical device that uses neuromodulation to aid in the reduction of symptoms associated with opioid withdrawal through stimulation of branches of cranial nerves V (Trigeminal), VII (Facial), IX (Glossopharyngeal), X (Vagus) and the occipital nerves.

[figure not shown]

Figure 1. Overview of Bridge™ System. **A.** Bridge™ kit. The kit contains all items required for device placement which includes: a. Stimulator with inserted but not activated batteries, b. wire harness for use with the stimulator, c. eight round bandages, d. two stimulator adhesive, e. compound benzoin tincture, f. two alcohol swabs, g. Sureprep® protective wipe, h. Tegaderm™, i. biohazard bag, j. patient information card, k. tweezer, l. surgical marker, m. transilluminator/medical light, n. *Quick Reference Guide*, o. *Directions for Use*. **B.** Bridge™ device. The device is composed of the stimulator which is the power source of the device and placed behind the ear and the wire harness with four electrodes to be placed on different zones of the ear for stimulation. **C.** Bridge™ device worn by a patient.

Impact of Bridge™ device as a non-pharmacological approach to treat opioid withdrawal in opioid use disorder (OUD) subjects in an inpatient treatment center**DENE0001**

The main components of the Bridge™ device are the Bridge stimulator (Fig. 1. A. a.), which is the power source of the device and the wire harness (Fig. 1. A. b.), which transmits the signal to the attached arrays. The kit includes the following additional items required for proper placement, securement, and disposal of the device:

- Eight round bandages to place over the arrays and secure the appliance leads (Fig. 1. A. c.)
- Two stimulator adhesives used to affix the stimulator to patient skin (Fig. 1. A. d.)
- Compound benzoin tincture, which is a disinfectant and adhesive used to keep the implanted electrodes in place, avoiding array migration (Fig. 1. A. e.)
- Two alcohol swabs to clean and disinfect the skin of any oils and makeup (Fig. 1. A. f.)
- Sureprep® protective wipe to help protect skin and aid adhesion (Fig. 1. A. g.)
- Tegaderm™ for additional coverage of stimulator and wires if need (Fig. 1. A. h.)
- Biohazard bag for device disposal (Fig. 1. A. i.)
- Patient information card (Fig. 1. A. j.)
- Disposable tweezers to hold array for implantation (Fig. 1. A. k.)
- Surgical marker used to mark transplantation sites (Fig. 1. A. l.)
- Transilluminator to visualize and isolate the neurovascular bundles for proper array placement (Fig. 1. A. m.)
- *Quick Reference Guide* (Fig. 1. A. n.)
- *Direction for Use* (Fig. 1. A. o.)

As shown in Figure 1.C, the Bridge™ wire harness has four wires: three gray wires with single-pin electrodes and one white wire with a multi-pin array, which serves as a ground wire. Two of the single-pin electrodes and the multi-pin electrode are placed on the front (ventral) of the ear and one single-pin electrode is placed on the back (dorsal) of the ear. The stimulator is placed behind the ear and percutaneous electrodes are positioned using the transilluminator. The use of transillumination is necessary to locate, visualize, and isolate the auricular neurovascular bundles. The medical marker can then be used to mark the final locations of implantation of the electrode arrays. Implantation sites of the electrodes should not be directly over a large arterial branch but rather within 1 mm to avoid bleeding. This assures maximum energy transfer, minimum tissue resistance, and minimizes patient discomfort. As shown in Figure 2, the first electrode implantation zone is the ear lobe (lobule) for the multi-pin ground electrode. The second zone is anterior and superior to the tragus, which allows for the simultaneous stimulation of the Trigeminal nerve and a branch of the superficial temporal artery. The third zone is the superior one-third ventral aspect of the ear (anterior scaphoid fossa). The fourth and final zone is the dorsal aspect of the ear (posterior aspect of the helix) which covers large branches of the posterior auricular artery leading to the external ear. The Bridge device has a 120-hour runtime and has a pulse sequence of 2 hours on and 1 minute off with the cycle repeating over the 120-hour runtime. The sham device is similar to the active device, except that the stimulator does not deliver any current.

[figure not shown]
Impact of Bridge™ device as a non-pharmacological approach to treat opioid withdrawal in opioid use disorder (OUD) subjects in an inpatient treatment center**DENE0001**

Figure 2. Overview of Bridge™ Placement. **Zone 1.** Great Auricular Nerve. Implantation of multi-pin array in the center of the ear lobe. **Zone 2.** Auricular Branch of the Vagus Nerve. Implantation of one of the single-pin electrodes in the area anterior and superior to the tragus. **Zone 3.** Auriculotemporal Nerve. Implantation of the next single-pin electrode at the superior one-third ventral aspect of the ear. **Zone 4.** Lesser Occipital Nerve. Implantation of the last single-pin electrode at the dorsal side of the triangular fossa.

Refer to Investigator Brochure and User's Manual for complete device instructions and descriptions.

4. JUSTIFICATION FOR CLINICAL INVESTIGATION DESIGN PLAN

Opioid addiction is a serious public health issue that negatively impacts many communities around the world. Opioid use (including prescription opioids and heroin) kills many people in the U.S. each year. From 1999 to 2018, opioids were involved in more than 446,000 deaths³, approximately 232,000 of which were the result of overdoses related to prescription opioids.⁴ In 2018, the most recent year for which data is available, approximately 47,000 deaths involved opioids, almost 15,000 of which involved prescription opioids.³

The current standard of care treatment for patients suffering from OUD is participation in a medication assisted treatment (MAT) program. However, one of the obstacles of reaching to an MAT program is the fear of enduring opioid withdrawal symptoms associated with the abrupt discontinuation of opioid use during the detoxification phase. Acute opioid withdrawal is often accompanied by painful, often severe flu-like symptoms including but not limited to sweating, gastrointestinal upset, tremors, anxiety, agitation, insomnia, and joint pain lasting for up to two weeks. Accordingly, voluntary discontinuation by opioid users is a long and challenging process. It has been estimated that less than 20% of the more than two million people suffering from OUD in the U.S. are receiving treatment.⁵

Bridge™, which received FDA clearance in 2017 and aids in relieving opioid withdrawal symptoms, may be the solution to helping individuals who suffer from OUD. A 2018 study by Miranda and Taca,⁵ in a cohort of 73 OUD individuals during the induction phase of opioid withdrawal, demonstrated that Bridge™ reduced acute opioid withdrawal symptoms within 15-30 minutes and provided continuous relief for the duration of five days of device wear. In this study, withdrawal symptom evaluated through comparison of *COWS* scores at various time points after device placement to baseline showed 84.6% reduction in *COWS* after the first hour of Bridge™ use and 97.1% after five days.⁵ By aiding in the reduction of withdrawal symptoms, Bridge™ has the potential to help OUD patients with successfully transitioning away from opioids and into an appropriate treatment plan.

CLINICAL INVESTIGATION PLAN

Impact of Bridge™ device as a non-pharmacological approach to treat opioid withdrawal in opioid use disorder (OUD) subjects in an inpatient treatment center

DENE0001

The intent of this study is to investigate the efficacy of Bridge™ in alleviating withdrawal symptoms in a prospective, sham-controlled setting. *COWS* and *SOWS* will be used to assess the severity of opioid withdrawal symptoms and as an outcome measure to assess treatment effect. *COWS* is a validated, clinically relevant, and reliable objective measure of therapeutic effect and clinical benefits, which is widely used in drug treatment protocols to assess the signs, symptoms, and severity of acute withdrawal, while *SOWS* is a subjective measure^(6, 7).

5. BENEFITS AND RISKS OF THE INVESTIGATIONAL DEVICE, CLINICAL PROCEDURE, AND CLINICAL INVESTIGATION

Anticipated benefits: There may be direct benefits to subjects participating in the active Bridge™ arm. There are no anticipated benefits to subjects who receive the sham device.

Device risks: Potential risks of percutaneous therapies, generally, include bleeding or infection at the puncture site, pain or skin irritation at the application site. Refer to the *Instructions for Use* for safety information, warnings, and cautions.

Contraindications: The device is contraindicated for use by patients with cardiac pacemakers, hemophilia, and psoriasis vulgaris. The device is also contraindicated for use in patients with a previous history of sensitivity to compound benzoin tincture, which is used to attach the electrodes to the ear.

Risk mitigation: Device shall be placed on intact skin only and subjects with cardiac pacemakers, hemophilia, and psoriasis vulgaris will be excluded from the study.

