7.5.2. Exclusion Criteria

- Participant requires tapering from another substance at entry to treatment
- Participant is pregnant or lactating
- Participant has a history of hemophilia or psoriasis vulgaris
- Participant has a cardiac pacemaker implant device
- Participant has irritated or broken skin at the site of intended device placement
- Participant is currently participating in, or was enrolled in another clinical trial within the last 30 days
- Participant has a history of poor wound healing
- Participant has a severe autoimmune disease or uncontrolled diabetes
- Participant has an open wound/abscess infection/MRSA
- Participant has a history of a chronic pain in the last 90 days

Impact of Bridge™ device as a non-pharmacological approach to treat opioid withdrawal in opioid use disorder (OUD) subjects in an inpatient treatment center

DENE0001

- Participant has a serious medical condition which in the judgment of the principal investigator or his/her designee would make study participation unsafe, or would make intervention compliance difficult
- Participant has a psychiatric illness (bipolar disorder, schizophrenia, or other psychotic disorder, active suicidal ideation with a plan within the last month or suicide attempt)

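### Section 5 makes benzoin tincture sensitivity a contraindication, but neither exclusion list contains it, so the eligibility rule as written admits a contraindicated participant

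*Combined protocol and SAP*

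**What the plan says.** Section 5 gives the contraindications in two consecutive sentences. The first is "The device is contraindicated for use by patients with cardiac pacemakers, hemophilia, and psoriasis vulgaris". The second adds a fourth: "The device is also contraindicated for use in patients with a previous history of sensitivity to compound benzoin tincture". The same sentence explains that the tincture attaches the electrodes to the ear.

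The risk-mitigation paragraph that follows requires placement on intact skin and says that "subjects with cardiac pacemakers, hemophilia, and psoriasis vulgaris will be excluded from the study". It does not mention the tincture.

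Section 7.5.2 turns the first three contraindications into exclusion criteria: "Participant has a history of hemophilia or psoriasis vulgaris" and "Participant has a cardiac pacemaker implant device". The synopsis in Section 2 carries the same 12 exclusion criteria. Neither list refers to benzoin, to adhesives or to allergy of any kind.

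Section 3 lists among the kit items needed for placement and securement "Compound benzoin tincture, which is a disinfectant and adhesive used to keep the implanted electrodes in place". It describes the sham as similar to the active device except that its stimulator delivers no current. Sections 7.1 and 7.4 say that the two are identical in appearance.

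**The concern.** Contraindications and exclusion criteria serve the same purpose in a device trial: anyone the plan says should not receive the device should be stopped at eligibility. Here the plan carries three of its four contraindications through to the exclusion lists and drops the fourth without giving a reason.

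Safety comes first. A person with known sensitivity to the tincture could be consented on arrival, pass every listed criterion, and have the device attached with a substance to which they are known to react. Exposure is not momentary, since the runtime is 120 hours and completion means five days of wear. If that person is allocated to sham, Section 5 anticipates no benefit to set against the risk.

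A lesser consequence concerns the data. Skin irritation at the application site is an anticipated adverse event (Sections 5 and 14.2). Under Section 7.6.8, a participant who asks for removal before five days is withdrawn from further assessments, so a reaction could also cost later COWS and SOWS measurements.

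**Working it through.** The plan gives no figure on this point, so the check is an item-by-item comparison of the places where the four contraindications should appear.

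| Contraindication in Section 5 | Section 5 risk mitigation | Synopsis exclusions | Section 7.5.2 exclusions |
|---|---|---|---|
| Cardiac pacemaker | yes | yes | yes |
| Hemophilia | yes | yes | yes |
| Psoriasis vulgaris | yes | yes | yes |
| Benzoin tincture sensitivity | no | no | no |

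Three of four contraindications are carried through, and the fourth is missing from all three places. Neither exclusion list shows a redaction, so blacked-out text does not explain the gap.

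**Could another listed criterion cover it?** Two come near.

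- "Participant has a serious medical condition which in the judgment of the principal investigator or his/her designee would make study participation unsafe" is discretionary and confined to serious medical conditions. A history of sensitivity to a topical agent is not plainly one.
- "Participant has irritated or broken skin at the site of intended device placement" concerns the state of the skin at screening. A sensitive person with intact skin passes it.

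**Does the enrollment rule look beyond the lists?** No. Section 7.5.4 defines an enrolled participant as one who meets every inclusion criterion, meets no exclusion criterion and has been given an identification number. Contraindications are not mentioned.

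**Would a later step catch it?**

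- Section 7.6.2 records medical history, but it specifies no allergy question and no action on the answer.
- Section 7.6.1 has patients approached on arrival and the device placed immediately, before comfort medications are provided.
- Section 7.6.4 keeps the personnel who place the device out of subject care.
- Section 7.7 has the monitor verify adherence to the inclusion and exclusion criteria. Enrolling a benzoin-sensitive person breaches none of them, so that check would not flag it.

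**Who is exposed?** In the active arm, Section 3 puts the tincture in the kit and Section 5 says it attaches the electrodes. For the sham arm this is an inference: if the device differs only in current, its electrodes would be attached in the same way. The plan does not list the contents of a sham kit, and Section 7.6.6 mentions only an unspecified adhesive for the generator. If the inference is right, all 48 planned participants (24 per arm) are exposed. The number of them who are sensitive is unknown, because the documents give no prevalence.

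**The case against.** The best counter-argument is that the protocol is more than its exclusion list. The contraindication stands in Section 5, and Section 13 binds the investigator to all stipulations of the protocol. Sections 3 and 5 send staff to the Investigator Brochure, the User's Manual and the Instructions for Use, and medical history is taken before randomization. Neither the CRF nor the medical-history form is available, so the site may in fact ask about adhesive or topical sensitivity. On this view an alert investigator would not place the device on a sensitive person.

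Part of this stands. The safeguards make exposure less likely, and the accurate statement is that benzoin sensitivity is not a listed exclusion. It cannot be said that nobody will ask about it. None of these safeguards is an eligibility rule, however, and eligibility is where the plan chose to act on the other three contraindications.

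It is also fair to say that the counts do not measure risk. One in four is a share of list items, and 48 is the whole planned sample, not the number at risk. Sham exposure is inferred.

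The effect on outcomes is likely to be slight. Withdrawal under Section 7.6.8 follows a participant's request, data collected up to that point may still be used, and Section 7.5.4 allows replacement. Section 8 already provides for heavy dropout. If both arms receive the tincture, there is no reason to expect loss to differ between them for this cause.

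Finally, the application-site harms that the plan names are bleeding, infection, pain and skin irritation; no serious benzoin reaction is described. That bears on how grave a case might be. It does not remove the conflict between Section 5 and the exclusion lists.

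**Conclusion.** The concern holds. Section 5 identifies four groups for whom the device is contraindicated, and the eligibility rule as written admits one of them. This follows directly from the text and needs no assumption. Exposure in the sham arm rests on the sham being attached like the active device, which is a strong inference from its description. The number of participants affected cannot be estimated from the documents and may be small.

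The matter is one of participant safety and consistency within the protocol. It does not change the sample size, power, alpha or primary comparison, and any loss of outcome data is secondary. It should still be corrected before enrollment, because the plan's own text identifies the people at risk and its eligibility rule does not act on that.

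**What to change.** Reconcile the passages. The risk-mitigation sentence in Section 5, the synopsis exclusion list and Section 7.5.2 should agree with the contraindications that Section 5 states. The sponsor should then confirm that the eligibility CRF has an item for each one, adding an item for benzoin sensitivity if there is none, so that the check is documented before randomization and can be monitored. It would also help to state in Section 7.6.6 whether the tincture is applied in both arms, which would settle the inference about the sham.

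The cost is about one line in each list, one CRF item and one question at screening, with a negligible effect on recruitment expected. If the protocol is already approved, the change needs the amendment and IRB approval described in Section 10. No statistical quantity has to be recalculated.

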6. OBJECTIVES OF THE CLINICAL INVESTIGATION

The purpose of this prospective study is to investigate the efficacy of the Bridge™ device in reducing the symptoms of opioid withdrawal in a blind comparison to a sham device.

Primary hypothesis:

- Participants on the active Bridge™ device will show significant reduction in the severity of opioid withdrawal signs and symptoms, assessed using the *COWS* score, in comparison to the sham group.

Secondary hypothesis:

- Participants on the active Bridge™ device will show significant reduction in the severity of opioid withdrawal signs and symptoms, assessed using the *SOWS* score, in comparison to the sham group.

CLINICAL INVESTIGATION PLAN

Impact of Bridge™ device as a non-pharmacological approach to treat opioid withdrawal in opioid use disorder (OUD) subjects in an inpatient treatment center

DENE0001

7. DESIGN OF THE CLINICAL INVESTIGATION

7.1. General

This is a two-arm, prospective, randomized, double-blind, sham-controlled clinical trial. The sham control device will be identical in appearance to the active device but will not deliver electrical current. Enrolled participants will be randomly assigned an active or sham Bridge™ device based on the randomization scheme provided by the sponsor. Sponsor will sequentially number devices to ensure allocation concealment. Research staff placing the device will not collect data on the CRF for that subject to prevent any bias in data collection. Unblinding of participant's treatment assignment will only be broken if the health of the participant is at risk as determined by an onsite medical doctor.

Overview of tasks to be completed

1. Prescreening, consenting, eligibility verification, demographic, medical history data collection
2. Baseline assessments (*COWS, SOWS,* [REDACTED])
3. Randomization and Bridge placement
4. Assessments throughout the course of the study (See Table 1)
5. Study Follow-Up

7.2. Endpoints

Primary endpoints:

- Assess change in *Clinical Opiate Withdrawal Scale (COWS)* score

Secondary endpoints:

- Assess change in *Subjective Opiate Withdrawal Scale (SOWS)* score

CLINICAL INVESTIGATION PLAN

Impact of Bridge™ device as a non-pharmacological approach to treat opioid withdrawal in opioid use disorder (OUD) subjects in an inpatient treatment center

DENE0001

